## **Serious Adverse Experience Reporting**

Adverse events will be documented per the University Hospitals Cleveland Medical Center, Human Research Protections guidelines, reported to the IRB, DSMB and the sponsor. The collection period for all SAEs will begin after informed consent is obtained and end after procedures for the final study visit have been completed.

## **Medical Monitoring**

[name] and/or [name] should be contacted directly to report medical concerns or questions regarding safety.

## **DISCONTINUATION OF SUBJECTS**

### **Early Discontinuation of Study Drug**

A subject may be discontinued from study treatment at any time if the subject, the investigator, or the Sponsor feels that it is not in the subject's best interest to continue. The following is a list of possible reasons for study treatment discontinuation:

Subject withdrawal of consent (or assent)

Subject is not compliant with study procedures

Adverse event that in the opinion of the investigator would be in the best interest of the subject to discontinue study treatment

Protocol violation requiring discontinuation of study treatment

Lost to follow-up

Sponsor request for early termination of study

Positive pregnancy test (females)

If a subject is withdrawn from treatment due to an adverse event, the subject will be followed and treated by the Investigator until the abnormal parameter or symptom has resolved or stabilized.

All subjects who discontinue study treatment should come in for an early discontinuation visit as soon as possible and then should be encouraged to complete all remaining scheduled visits and procedures.

All subjects are free to withdraw from participation at any time, for any reason, specified or unspecified, and without prejudice.

Reasonable attempts will be made by the investigator to provide a reason for subject withdrawals. The reason for the subject's withdrawal from the study will be specified in the subject's source documents.

## **DATA SAFETY MONITORING**

A Data Safety Monitoring Board (DSMB) will be established to review data relating to safety and efficacy, to conduct and review interim analyses, and to ensure the continued scientific validity and merit of the study. Reviews will be conducted by the DSMB every 3 months for the purpose of monitoring study conduct and assessing patient safety.

## STATISTICAL METHODS AND CONSIDERATIONS

Prior to the analysis of the final study data, a detailed Statistical Analysis Plan (SAP) will be written describing all analyses that will be performed. The SAP will contain any modifications to the analysis plan described below. General Statistical Considerations: All the tests are two-sided. We use log transformations for most continuous measures, and arc-sin square root transformations for percentages, both of which have excellent variance stabilizing properties for pooling variance.

**Analysis Plan:** After distributions are checked and outliers are investigated for veracity, descriptive statistics by treatment arm will be reported for patient demographics and important potential confounding variables at baseline. These will include age, gender, BMI, baseline blood pressure, HbA1c, 24-hour urine Na, plasma and renin/aldo activity at baseline, HOMA-IR, HDL and non-HDL cholesterol. To analyze these data (primary end points and secondary outcome measures), linear mixed models with group (drug/placebo), baseline plaque volume, time points (before/after), stratification variables (age, high-risk feature) and other potential confounders (such as demographics and other comorbidities) as well as a patient random effects (to account for the correlation of measures within same patient) will be used. Different covariance structures will be used and best model will be selected based on AIC criteria by first fitting most complicated mean structure model, selecting the best covariance structure, then selecting the best mean structure, using SAS procedure GLIMMIX or MIXED) and convergence and model performance will be evaluated using SAS fit statistics (e.g. AIC criteria). Clinically relevant interactions will also be included in the models. Forward stepwise selection followed by backward elimination will be used to retain features with the greatest combined prediction power while maintaining parsimony using a training data set. Traditional methods, such as AIC and BIC involve a combinatorial optimization problem, which is NP-hard, with computational time increasing exponentially with the dimensionality. The expensive computational cost makes traditional procedures infeasible for high-dimensional data analysis. To overcome this, penalized likelihood maximization and penalized risk minimization have been intensively used for classification. Penalized methods with  $L_p$ -penalty, especially when  $p \leq 1$ , automatically perform variable selection by removing predictors with very small estimated coefficients. Fan et al. proposed SCAD-penalty with better oracle properties 131 . It automatically selects features and avoids excessive estimation bias compared to  $L_1$ -penalty. We will use penalized methods for classification in order to avoid over-fitting problems by producing sparse solutions via feature selection.

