### **STUDY OBJECTIVES**

#### **Primary Objective**

Evaluate the impact of Spironolactone in reducing atherosclerosis plaque as measured by change in percent total atheroma volume (PAV) in thoracic aorta with Spironolactone vs. placebo.

[figure not shown]

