## CRITERIA FOR EVALUATION

### Co-Primary Efficacy Endpoints

The co-primary outcome measure is change in 24-hour SBP in Spironolactone treated patients versus placebo and percent change in total atheroma volume (PAV) in thoracic aorta of Spironolactone vs placebo.

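### For the plaque endpoint, the Aim 1 mixed model appears to use the baseline scan both as a response row and as a covariate; it should be used once.

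*Combined protocol and SAP*

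**What the plan says.** The model is in the Combined protocol and SAP, Statistical Methods and Considerations, Aim 1, Analysis Plan. Its terms include "linear mixed models with group (drug/placebo), baseline plaque volume, time points (before/after"), and it adds "patient random effects (to account for the correlation of measures within same patient"). A before/after factor with a patient random effect implies more than one response row per patient. Table 4 (Main Study Phase) schedules MRI twice, so plaque has one before row and one after row.

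Three points are left open:

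- **Covariance:** "Different covariance structures will be used and best model will be selected based on AIC criteria".
- **Interactions:** "Clinically relevant interactions will also be included in the models". None is named, so neither group-by-time nor baseline-by-time is specified.
- **Outcome and scale:** the Primary Objective has "change in percent total atheroma volume (PAV) in thoracic aorta with Spironolactone vs. placebo", while Co-Primary Efficacy Endpoints has "percent change in total atheroma volume (PAV) in thoracic aorta". The general considerations log most continuous outcomes and apply an arcsine square root to percentages. No scale is given for the covariate.

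The same model serves all outcomes: "To analyze these data (primary end points and secondary outcome measures"). The section also says that a detailed SAP will follow.

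**The concern.** When a baseline value is both a covariate and one of two responses, a single slope has to serve both rows. In the before row the baseline predicts itself perfectly; in the after row it predicts with slope rho. The fitted slope settles between the two, and this makes a patient's two residuals negatively correlated. An ordinary random intercept can represent only zero or positive correlation, so its variance goes to zero. The rows are then treated as independent, and the before-to-after difference looks more precise than it is.

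The AIC search adds a second problem. A covariance structure with a separate before-row variance can fit that row exactly, and the criterion rewards it without limit.

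At stake are the two-sided 5% error rate on a co-primary endpoint and the stability of the model selection.

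**Working it through.** **Inputs.** From Aim 1 and the general considerations: 52 per group, two-sided alpha 0.05, 80% power, CV 0.83, 1.5-fold difference, 20% loss, 130 recruited. The documents give no before/after correlation, so rho is assumed, from 0.3 to 0.9. Steps 1 to 4 also assume that the covariate equals the before response on the same scale.

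**The plan's own figure.** Log-scale SD = sqrt(ln(1 + 0.83²)) = 0.724, and the difference is ln 1.5 = 0.405. The normal formula gives 2 × (1.960 + 0.842)² × 0.724² / 0.405² ≈ 50.04, rounded up to 51. The noncentral-t version gives 52, as stated, and 104/0.80 = 130. This is a two-group comparison with no rho in it, so it neither reveals the fault nor changes with the fix.

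**1. Residuals.** Take unit variances before and after.

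- Shared slope: b = (1 + rho)/2.
- Residual covariance: (1 − b)(rho − b) = −(1 − rho)²/4. It is negative, so a bounded random intercept is set to zero.
- Sum of the two residual variances: (1 − rho)(3 + rho)/2.
- True variance of the change: 2(1 − rho).
- Reported/true variance of the group-by-time contrast: (3 + rho)/4.

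**2. Size with complete pairs, 52 per arm.** Type I error by formula is 2Φ(−1.96 × SE ratio). The simulated column gives the spread over separate null simulations with group-by-time in the model.

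| rho | (3 + rho)/4 | SE ratio | Type I, formula | Type I, simulated |
|---|---|---|---|---|
| 0.3 | 0.825 | 0.908 | 7.5% | 6.9–7.9% |
| 0.5 | 0.875 | 0.935 | 6.7% | 6.2–6.8% |
| 0.7 | 0.925 | 0.962 | 5.9% | 5.9–6.1% |
| 0.9 | 0.975 | 0.987 | 5.3% | 5.2–5.4% |

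The intercept variance was zero in 90–100% of runs. Without the covariate, type I error was 4.8–5.3%.

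**3. Departures from step 2.** With unequal variances the ratio never exceeds 1, and it equals 1 only if the regression slope of after on before is 1. With 65 per arm, the planned 20% loss and the dropouts' before rows kept, the SE ratio was 0.87 and type I error 8.6% (rho 0.5) and 8.9% (rho 0.8). The plan does not say whether those rows are kept.

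**4. Likelihood with a separate before-row variance.** At slope 1 every before residual is zero. One simulated data set gave:

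| Before-row SD | 1 | 0.1 | 0.01 | 0.001 | 0.0001 |
|---|---|---|---|---|---|
| ML log-likelihood | −190 | 46 | 286 | 525 | 765 |
| REML log-likelihood | −202 | 28 | 261 | 493 | 726 |

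Neither has a maximum, so AIC falls without limit.

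**5. When the faults go away.**

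- *Covariate not identical to the before response.* The standard error is correct in large samples once their correlation is below 2·sqrt(rho)/(1 + rho): 0.843 at rho 0.3, 0.943 at 0.5, 0.994 at 0.8, 0.9986 at 0.9. At correlation 0.95, simulated type I error was 5.2% (rho 0.5) and 5.1% (rho 0.8). The unequal-variance likelihood then peaked at about −146, near a before-row SD of 0.3 among the values tried.
- *Residual compound symmetry with negative covariance allowed.* SE ratio 0.99 and 1.00, type I error 5.3% and 5.0% (rho 0.5 and 0.8).
- *Baseline-by-time added.* SE ratio 0.99 at both, type I error 5.2% at both.

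**6. Group main effect only.** If only the listed terms are fitted and group is tested, reported/true variance is (3 + rho)/(2(1 + rho)): 3.3/2.6 = 1.27 at rho 0.3 and 3.9/3.8 = 1.03 at rho 0.9. Simulated type I error was 2.6%, 3.4%, 4.1% and 4.6% at rho 0.3, 0.5, 0.7 and 0.9. The group coefficient is then half the ANCOVA estimate.

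**The case against.** A reader might infer that the planned test is anti-conservative whatever is done, and that the AIC search must break down. The documents do not support either as an unconditional statement.

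- **Identity is not stated.** The response is mostly described as a percentage and may be transformed; the covariate is called a volume, with no scale. Logging one and not the other could be enough. For a lognormal measure with CV 0.83, taken as between-patient spread, the correlation of the value with its log is 0.724/0.83 = 0.87. That is below the threshold at rho 0.5 and above, though not at 0.3. This objection stands, and it makes the finding conditional.
- **The contrast is not named.** Without group-by-time the error is in the other direction. It also follows that the covariate cannot be called useless in general: it leaves the estimate unchanged only for group-by-time with complete pairs.
- **The covariance is not fixed.** One of the structures tried might allow negative covariance. That is possible, but nothing commits the analyst to it.
- **A degenerate fit would be noticed.** The plan says convergence will be checked, so this is more likely a conspicuous failure than a silent bias. The check still supplies no replacement model.
- **The size is small at high rho.** With complete pairs this is true. It is less reassuring if dropouts' before rows are kept.
- **A later SAP is promised.** That is an opportunity to correct the text and does not itself correct it.

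A reader might also extend the point to blood pressure and HOMA-IR, because one sentence covers all outcomes. For those, baseline plaque is not the before row, and neither consequence follows.

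**Conclusion.** The point holds in conditional form, for the plaque endpoint only. As written, the model lists a baseline plaque covariate beside a before row that is already a response.

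The understated standard error requires three things together: the covariate is the before response on the same scale, the random intercept is bounded at zero, and group-by-time is the tested contrast. It then amounts to roughly 1% to 9% of the standard error with complete pairs and equal variances, over an assumed rho of 0.9 to 0.3. The unbounded likelihood requires the same identity and a covariance structure with its own before-row variance.

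The text rules out none of these conditions and settles none of them. The inflation is modest, but the endpoint is co-primary and the correction is simple, so the change should be made.

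**What to change.** State that no plaque measurement appears as both response and covariate in one model, and choose one of two forms:

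1. Keep before and after plaque as response rows, name group-by-time as the treatment contrast, and remove baseline plaque volume from the covariates.
2. Make the exit value (or the change) the only response, with baseline plaque as a covariate and group as the treatment contrast.

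In either case, state the scale of the plaque outcome and fix one covariance structure in advance where there are two rows. Simulated type I error with baseline used once was 5.0–5.3%. Form 2 has the smaller true standard error: at rho 0.5, with unit variances and 52 per arm, the simulated SD of the estimate was 0.172, against 0.199 for the before/after contrast.

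The cost is one line in the analysis plan. No new data are needed, and 52 per group and 130 in total are unchanged. The downside is that the plaque p-value may become slightly less favourable than under the understated standard error.

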**Aim 2a: To evaluate the functional significance of candidate miRNAs.**

**Analysis Plan:** An interaction contrast in an ANOVA model will be used to test the effects of overexpression of miRNAs (miR mimic) or antagomiRs in various experiments where we will test the effect of miRNAs alone or in the presence of LPS or IL4/13. The effect of various interventions on NR3C2 gene expression and MR protein expression as well as markers of alternate activation will be tested.

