Fifteen miRNAs including 2 unique miRNA families (miR-30 and miR129) were identified that bound to 11 distinct sites on the 3'-UTR. These miRNAs were then analyzed in 10 miRNA prediction algorithms (Diana, MicroInspector, Miranda, mirtarget2, mitarget, nbmirtar, pictar, pita, rna22, rnahybrid). miRNAs that were common to at least 5 different prediction algorithms were identified. Based on this analysis, we investigated the expression of miRNAs initially identified in-silico, in human monocytes and then investigated their regulation in monocytes derived from a cohort of patients with atherosclerosis (derivation cohort, n=10; mean age=65±6 years) using an expression array with >600 miRNAs (Nanostring Technologies. All patients in the derivation cohort were receiving ACEI/ARB/statin therapy and were compared to control subjects without risk factors for atherosclerosis (n=6 per group). We used a miRNA expression array (Nanostring Technologies, CA) that provides quantitative assessment of >600 human miRs. miR's regulated in atherosclerosis were defined as those that were highly regulated (p<10-10 vs. control subjects). The data set was filtered for outliers and analyzed. The putative miRNAs that target NR3C2, are expressed in monocytes AND are downregulated in atherosclerosis. We then analyzed

the relationship of miRNAs obtained in the derivation cohort, with aortic plaque measured by MRI. Correlation analysis with baseline atherosclerosis revealed that multiple miRs correlated with atherosclerosis plaque burden at baseline after adjustment of baseline covariates (age, gender, blood pressure and LDL cholesterol). This included 31 miRNAs involved in NR3C2 regulation ( $r^2 = 0.35$ ) as well as several candidate miRs unrelated to MR expression (Down-regulated=miR-27,  $r^2 = 0.36$ ; miR-125,  $r^2 = 0.25$ ; miR-124,  $r^2 = 0.20$ ; miR-7  $r^2 = 0.19$ ; Up-regulated: miR-223.  $r^2 = 0.25$ ; mir-126.  $r^2 = 0.22$ ; miR-1720,  $r^2 = 0.15$ ).

**Regulation of NR3C2-3UTR Luciferase Reporter:** NR3C2 3-UTR was cloned downstream of a mammalian promoter-luciferase system and co-transfected in HeLa cells with plasmids expressing pmiR-19b and pmiR-124 have shown that 124 but not 19b reduced luciferase activity by more than 50%. Studies examining other miRNAs in HeLa cells are currently ongoing in the laboratory.

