## Secondary Objectives

Evaluate the functional significance of candidate miRNAs. Compare monocyte polarization and inflammatory gene expression at 6-weeks. Evaluate miRs expression to predict atherosclerosis and response.

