### Secondary Efficacy Endpoints

Change in central aortic SBP, Change in central aortic DBP, Change in central aortic Mean BP, 24-hour mean ambulatory BP, 24-hour ambulatory diastolic blood pressure, and HOMA-IR.

Evaluate miRs involved in regulating MR expression and differentially regulated miRs as predictors of disease progression and response.

Compare monocyte inflammatory activation in Spironolactone vs placebo at 6-weeks.

Investigate pre-miR/mimics and antagonomirs to regulate NR3C2 expression and alternate macrophage phenotype in human macrophages.

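### Aim 2a names only an interaction contrast, which cannot detect a miRNA effect on NR3C2/MR expression that is the same fold change with and without LPS or IL4/13

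*Combined protocol and SAP*

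**What the plan says.** The combined protocol and SAP gives Aim 2a a short analysis plan under Statistical Methods and Considerations.

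- **Aim.** The heading reads "To evaluate the functional significance of candidate miRNAs", and the same goal stands under Secondary Objectives.
- **Named test.** "An interaction contrast in an ANOVA model will be used to test the effects of overexpression of miRNAs (miR mimic) or antagomiRs". No other contrast is named for this aim.
- **Layout.** The experiments are ones "where we will test the effect of miRNAs alone or in the presence of LPS or IL4/13".
- **Outcomes.** "The effect of various interventions on NR3C2 gene expression and MR protein expression as well as markers of alternate activation will be tested". This sentence names outcomes but no contrast.
- **Endpoint.** Secondary Efficacy Endpoints lists: "Investigate pre-miR/mimics and antagonomirs to regulate NR3C2 expression and alternate macrophage phenotype in human macrophages".
- **General rules.** "All the tests are two-sided", and the same section puts most continuous measures on the log scale. It also promises a detailed SAP, with any modifications, before the final analysis.

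Aim 2a states no replicate number, SD, effect size, power or alpha.

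**The concern.** Whether a mimic or antagomiR regulates NR3C2 is a question about treated versus control cells. It is answered by a main effect averaged over stimulus conditions, or by a simple effect within one condition. An interaction contrast answers a different question: whether LPS or IL4/13 changes the size of that effect.

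The two can disagree completely. A miRNA that suppresses NR3C2 equally in resting and stimulated macrophages is functional in the sense of the endpoint, yet has no interaction. Direct action of a miRNA on the NR3C2 transcript could well look like this. At stake is whether the one pre-specified contrast can support a conclusion on NR3C2 and MR protein. If the main or simple effect is brought in only after the data are seen, that result has no pre-specified test behind it.

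**Working it through.** The plan has no figure to reproduce for Aim 2a, so the check is algebra followed by an illustration.

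**1. What the contrast measures.** Take a 2x2 layout (miRNA or control, stimulus or none) with cell means m on the log scale.

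- Interaction = (m[miR, stim] − m[ctrl, stim]) − (m[miR, none] − m[ctrl, none])
- Main effect = average of the same two differences
- Simple effect = m[miR, none] − m[ctrl, none]

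If the miRNA effect is d in both conditions, the interaction is d − d = 0, while the main and simple effects both equal d. This needs no assumed SD or replication. With LPS and IL4/13 as two separate stimuli, it holds for each against no stimulus.

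**2. The scale matters.** Take a 50% fall from 100 to 50 without stimulus and from 200 to 100 with it.

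- Log scale: log(100/200) − log(50/100) = 0.
- Raw scale: (100 − 200) − (50 − 100) = −50.

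The zero result is therefore for equal fold effects analysed on the log scale, which the plan adopts for most continuous measures but does not confirm for these outcomes.

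**3. Illustration of size.** All inputs here are assumptions:

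- 2x2 layout with n independent cultures per cell.
- Two-sided alpha 0.05 (the plan states 0.05 for Aim 1 only).
- True effect 1 log2 unit (a 50% fall).
- SD 0.71, borrowed from the Aim 2c sample-size text. There it is a median SD in a miRNA classifier calculation on patients, and is not labelled log2.

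Standard errors, with error df = 4(n − 1):

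- Main effect: SD/√n. At n = 6: 0.71/√6 = 0.290.
- Simple effect: SD·√2/√n. At n = 6: 0.410.
- Interaction: 2·SD/√n. At n = 6: 0.580.

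Power from the noncentral t distribution, same effect in both conditions:

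| n per cell | Main effect | Simple effect, no stimulus | Interaction |
|---|---|---|---|
| 4 | 73% | 45% | 5% |
| 6 | 91% | 64% | 5% |
| 10 | 99% | 87% | 5% |

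If the effect is halved under the stimulus (1.0 without, 0.5 with), the main effect is 0.75 and the interaction is 0.5 in size. At n = 6 the power is 69% for the main effect and 13% for the interaction.

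**4. Same check without the borrowed SD.** With effects in SD units, an equal effect of 2 SD gives main-effect power of 86% at n = 3 per cell and 99.6% at n = 6. The simple effect gives 58% and 91%. The interaction stays at 5%. A simulation of 100,000 runs at n = 6 and 2 SD rejected 4.96% (interaction), 99.7% (main effect) and 90.9% (simple effect).

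**The case against.** Several points on the other side carry weight.

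- **The interaction is not said to be the sole test.** A reader might infer that a real effect on NR3C2 would be reported as absent, or the candidate declared non-functional. The text does not support that. It says miRNAs will be tested alone as well as with a stimulus, and that effects on NR3C2 and MR protein will be tested. A factorial ANOVA also ordinarily yields main effects, and nowhere is a null interaction equated with no function. This stands, and it limits the finding to a mismatch that could cause a miss.
- **The interaction suits half of the endpoint.** The Background has LPS with interferon driving classical activation and IL-4/IL-13 driving alternative activation. Preliminary Studies reports that IL-4 acted synergistically with loss of MR on alternate-activation markers. Synergy is an interaction, so for the phenotype markers the named contrast follows the protocol's own reasoning. This stands too; the mismatch concerns NR3C2 and MR protein expression.
- **The power figures rest on assumptions.** True. Layout, replication, effect and SD are all supplied from outside Aim 2a, and the 5% is simply alpha under a true null. The algebra in step 1 does not depend on them.
- **The reporter result is weak support.** It is tempting to cite the finding that "124 but not 19b reduced luciferase activity by more than 50" per cent as an effect seen without a stimulus. The protocol takes it from a published study, and it is a luciferase assay in HeLa cells, not human macrophages. It illustrates the kind of effect and proves nothing about this aim.
- **A later SAP is promised.** That gives a place for the correction, but does not supply the missing contrast.

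**Conclusion.** The concern holds in a limited form. The only contrast named for Aim 2a does not match the question of whether mimics and antagomiRs regulate NR3C2 and MR expression. For an effect that is the same fold change in every condition, analysed on the log scale, its rejection rate is 5% regardless of effect size or replication. A main-effect test of the same data would have roughly 73% to 99% power under the assumed 4 to 10 cultures per cell; those percentages are illustrative only.

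A real stimulus-independent effect could be missed if the named contrast is the test used. The documents do not establish that it will be missed, and the contrast remains reasonable for synergy on alternate-activation markers. The matter is confined to a secondary laboratory aim: the randomised comparison, the co-primary endpoints and the sample size of 130 are unchanged.

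**What to change.** In the Aim 2a analysis plan, or in the SAP before these data are analysed:

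1. For NR3C2 gene expression and MR protein expression, name mimic versus control and antagomiR versus control as the test. State in advance whether this is the main effect averaged over stimulus or the simple effect without stimulus, and that it is done on the log scale. The averaged effect has the smaller standard error; the simple effect is easier to interpret if the direction could change with the stimulus.
2. Keep the interaction contrast for whether LPS or IL4/13 modifies the effect, including synergy on the alternate-activation markers.
3. If cells from one donor are split across conditions, which the plan does not state, enter donor as a block.

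The cost is a few sentences of wording. No new experiments or patients are needed.
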